6.5 Pooling of Sites

In order to avoid sparse sites (sites with fewer than 5 randomized subjects) and the potential for too many levels for the explanatory variable of “site”, sites within a

geographic region (Canada/USA/Rest of World) with fewer than 5 randomized subjects will be pooled into a single pooled site for use in efficacy analyses. If a resulting pooled site still has fewer than 5 randomized subjects, it will be further pooled with the smallest remaining unpooled site from that geographic region. If the resulting pooled site still has fewer than 5 randomized subjects, it will be further pooled with the smallest pooled site from another geographic region. This pooling is estimated to make up approximately 15% of all enrolled subjects by the time that the first 600 subjects will have been enrolled.

7.0 EFFICACY ANALYSIS

Efficacy analyses are summarized in [Table 2](#).

7.1 Primary Outcome Variable Analysis

7.1.1 Primary Outcome

The primary endpoint used in this trial will be global disability as measured by the mRS at Day 90. Scores for the mRS range from 0 to 6, with 0 indicating no residual symptoms; 5 indicating bedbound, requiring constant care; and 6 indicating death. The mRS will be obtained at Day 5 (or discharge) and Days 30 and 90. Premorbid mRS status will also be obtained retrospectively at 24 hours.

The primary efficacy analyses will be conducted in the ITT population, defined as all subjects randomized into the trial with grouping by randomized treatment, regardless of treatment actually received. Deceased subjects will be included in the ITT population with a mRS score of 6. The primary endpoint used in this trial will be global disability, as measured by the mRS, at Day 90.

7.1.2 Statistical Hypothesis

The primary hypothesis is:

$$H_0: \pi_{NA-1} = \pi_{\text{placebo}} \text{ VS } H_a: \pi_{NA-1} \neq \pi_{\text{placebo}}$$

Where π_{NA-1} and π_{placebo} are the NA-1 and placebo population proportions of responders, defined as subjects whose Day 90 mRS score is ≤ 2 .

7.1.3 Primary Efficacy Analysis

The primary efficacy outcome is the overall proportion subjects experiencing a favorable functional outcome 90-days post-randomization; where favorable is defined as a mRS score of 0, 1, or 2. Subjects with favorable functional outcomes are defined as responders. Subjects missing the day 90 primary assessment for any reason will be considered non-responders for the primary analysis.

The primary hypothesis to be tested is that administration of NA-1 will result in an increase in the proportion of responders (as defined by a score of 0-2) at Day 90. The primary analysis will be a Wald test for treatment group difference in the primary outcome from a logistic regression adjusted for the 2 stratification variables (alteplase use, first declared thrombectomy device), and the 6 covariates used in the minimization (age, sex, baseline NIHSS score, baseline ASPECTS score, occlusion location, and site). This will be conducted on the ITT population at the 2-sided 0.05 significance level overall (for the trial), adjusted for the interim analysis per the O'Brien-Fleming boundary spending function.

The following SAS PROC LOGISTIC code will be implemented for the binary primary endpoint analysis:

```
proc logistic data=adqs;
  where ittf1 = 'Y' and qstest = 'mRS (binary)';
  class occloc alteplase thromb_app site
    trtp(param=ref ref='Placebo') ;
  model mRS = age sex blnihss blaspect occloc
    alteplase*thromb_app site trtp;
  oddsratio trtp;
run;
```

Where mRS is the binary independent functioning score made by dichotomizing mRS at 2: $mRS \leq 2$ = independent functioning. Occloc is the occlusion location (MCA vs. ICA), blnihss is the baseline NIHSS score (0-42), blaspect is the baseline ASPECTS score (0-10), alteplase is an indicator for having received IV alteplase treatment, thromb_app is the thrombectomy approach (stent retriever vs. aspiration device), alteplase*thromb_app is a 4-level stratification, site is investigative site, sex and age are subjects' sex (male/female) and age (years) at study entry, and trtp is the planned treatment.

All odds ratios (with Wald 95% C.I.s) and corresponding Wald test statistics will be summarized in a table, by select subpopulations. Actual proportions with and without independent functioning will be reported as will the proportions in each of the ordinal mRS categories.

Three supportive analyses to the primary analysis will be conducted: (1) the primary analysis reapplied to the Per Protocol population; (2) a re-randomization analysis to demonstrate that minimization did not bias the primary endpoint analysis. The later test will consist of rerunning the randomization 5,000 times on the original subjects' data and then performing the primary endpoint analysis on each of the re-randomized data sets. This will yield a distribution of 5,000 p-values that will correspond to the p-value distribution expected under the null hypothesis of no NA-1 effect. The p-value from the actual primary analysis will be compared to the distribution of randomization p-values. If (for example) the minimization was unbiased and actual p-value was 0.01, we would expect $P=0.01$ to be near the 1st percentile of the distribution of the 5000 p-values. A variant of this methodology was successfully used to validate the minimization in the ESCAPE trial.^[2] (3) The primary analysis will be repeated on the PP population using actual first endovascular approach (instead of declared approach).

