7.2.1 Key Secondary Outcome Analysis

A key secondary analysis of the ordinal mRS scores will employ a proportional odds model (POM) to test the hypothesis that, among randomized subjects, those who are treated with NA-1 will show a shift in their mRS score distribution at 90 days relative to the mRS distribution of the placebo subjects. The magnitude of the shift will be estimated as the common odds ratio (95% C.I.). Modified Rankin scores of 5 and 6 (bed-bound with severe disability, and death) will be collapsed into a single category representing severely limited functioning. A covariate-adjusted POM will be used to derive the common odds of improvement (i.e. the NA-1 vs. placebo “shift” in mRS score distributions). Model covariates will include all of the variables in the minimization algorithm, both stratification variables and covariates.

The following example SAS code can be used to fit the POM to the subjects’ mRS score:

```
ODS graphics on;
proc logistic data=adqs;
  where ittf1 = 'Y' and qstest = 'mRS (Ordinal)';
  class occloc alteplase thromb_app site
    trtp(param=ref ref='Placebo') ;
  model mRS = age sex blnihss blaspect occloc
    alteplase*thromb_app site trtp;
  effectplot interaction(x=trtp sliceby=mRS)/polybar;
  oddsratio trtp;
run;
```

Where “mRS” is the collapsed mRS scale values ranging from 0 to 5 (level 5 = 5+6 mRS combined), “occloc” is the occlusion location (ICA vs. MCA), “blnihss” is the baseline NIHSS score (0-42), “blaspect” is the baseline ASPECTS score (0-10), ‘alteplase’ is an indicator for having received IV alteplase treatment, thromb_app is the thrombectomy approach (stent retriever vs. aspiration device), alteplase* thromb_app is a 4-level stratification, “site” is investigative site, subject sex and age are the subjects’ sex and age at study entry, and “trtp” is the planned treatment (NA-1, placebo).

When SAS fits the POM, it runs a global test for a shift across all 6 mRS categories in the NA-1 group relative to the placebo; this is the test of the proportional odds (PO) assumption. The proportional odds assumption will be checked via the score test at an alpha-level of 0.15 and also using graphical methods to view the cumulative log odds for each mRS score. If the assumption holds, the POM estimates a single fixed odds ratio for the 5 cumulative binary endpoints defined as follows:

- a. The proportion of subjects with $mRS = 0$ vs. the proportion with $mRS > 0$

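### The SAS code for the primary model enters `alteplase*thromb_app` without main effects, so it fits one contrast (1 df) instead of the four randomization strata (3 df) that the SAP text promises

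*SAP*

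**What the plan says.** SAP 7.1.3 describes the primary analysis as a Wald test from a "logistic regression adjusted for the 2 stratification variables (alteplase use, first declared thrombectomy device") and for the six minimization covariates. Protocol 11.3 says the same. SAP 1.5 lists four randomization strata, formed by alteplase (yes/no) and initial approach (stent retriever or aspiration).

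The code is presented as binding: "The following SAS PROC LOGISTIC code will be implemented for the binary primary endpoint analysis". Its CLASS statement begins "class occloc alteplase thromb_app site" and continues with "trtp(param=ref ref='Placebo"), the only coding option given. The MODEL statement contains `alteplase*thromb_app` but neither `alteplase` nor `thromb_app` alone. The notes below the code state that "alteplase*thromb_app is a 4-level stratification" and that "alteplase is an indicator for having received IV alteplase treatment".

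SAP 7.2.1 gives the same CLASS and MODEL lines for the proportional odds model, offered as an example, and again says that "alteplase* thromb_app is a 4-level stratification". Table 2 writes the crossed term alone for the primary, secondary and tertiary models.

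**The concern.** In a model with an intercept, four strata take up three degrees of freedom. A crossed term of two 2-level factors supplies all three only if the main effects are also present, or if the factors are coded with a full set of indicators (GLM coding). The printed code has neither feature, so run as written it would not fit the model the text describes.

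This is the pivotal analysis for regulatory submission. A programmer who follows the code departs from the text, and one who follows the text departs from code that the SAP says will be used. The two models give different odds ratios and p-values. Choosing between them after unblinding would be hard to defend if the result lay near the final one-sided boundary of 0.024 (SAP 3.0). The re-randomization check in 7.1.3 repeats the primary analysis 5,000 times and would inherit the same term.

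**Working it through.** **1. The plan's own power figure.** Inputs from SAP 1.4 and 3.0: 52% versus 60.7%, 538 per arm, final one-sided level 0.024 (z = 1.977).
- Pooled SE = √(2 × 0.5635 × 0.4365 / 538) = 0.03024.
- Unpooled SE = √((0.52 × 0.48 + 0.607 × 0.393) / 538) = 0.03012.
- Power = Φ((0.087 − 1.977 × 0.03024) / 0.03012) = Φ(0.90) = 81.7%, as stated in SAP 1.4. A two-look calculation gives 81.8%.

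The design effect on the model scale is ln(0.607/0.393) − ln(0.52/0.48) = 0.435 − 0.080 = 0.355, an odds ratio of 1.43.

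**2. Degrees of freedom of the printed term.** SAS forms a crossed effect by multiplying the factors' columns.

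| Stratum | Alteplase (effect) | Device (effect) | Product (effect) | Product (reference) |
|---|---|---|---|---|
| Alteplase + stent | +1 | +1 | +1 | 1 |
| Alteplase + aspiration | +1 | −1 | −1 | 0 |
| No alteplase + stent | −1 | +1 | −1 | 0 |
| No alteplase + aspiration | −1 | −1 | +1 | 0 |

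- Effect coding: one column, 1 df; the strata are merged in two pairs.
- Reference coding: one column, 1 df; one stratum is set against the other three.
- GLM coding: four indicators, rank 3 beyond the intercept.
- With main effects added: 3 df under every coding.

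The documents do not state the PROC LOGISTIC default (effect coding), so it is a premise here. The conclusion would fail only under GLM coding, which the code does not request.

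**3. What the single contrast adjusts for.** In equal strata its product with the alteplase column averages (1 − 1 + 1 − 1)/4 = 0, and the same holds for device, so neither factor is adjusted. With an assumed 60% alteplase and 75% stent retriever, the effect-coded means are A = 0.2 and D = 0.5:
- correlation with alteplase = D(1 − A²)/√((1 − A²)(1 − A²D²)) = 0.48/√(0.96 × 0.99) = 0.49;
- correlation with device = A(1 − D²)/√((1 − D²)(1 − A²D²)) = 0.15/√(0.75 × 0.99) = 0.17.

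Some of each factor is therefore absorbed, by accident of the stratum sizes.

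**4. Size.** The documents give no stratum shares or prognostic effects, so these are assumed. Logistic simulation: N = 1120, treatment balanced within strata, true log OR 0.355, 3,000 runs per setting, two-sided test at |z| > 1.977, other covariates and the interim look omitted. Each cell shows the printed term versus four strata.

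| Prognostic log OR, alteplase / device | Shares (alteplase, stent) | Treatment log OR | Power | Type I error |
|---|---|---|---|---|
| 0.3 / 0.2 | 50%, 50% | 0.356 vs 0.360 | 83.3% vs 83.9% | 4.2% vs 4.6% |
| 0.3 / 0.2 | 60%, 75% | 0.353 vs 0.356 | 82.7% vs 83.0% | 5.1% vs 5.5% |
| 0.7 / 0.5 | 50%, 50% | 0.341 vs 0.356 | 81.0% vs 81.9% | 4.7% vs 5.1% |
| 0.7 / 0.5 | 60%, 75% | 0.344 vs 0.355 | 81.0% vs 81.5% | 5.4% vs 5.5% |
| 1.1 / 0.8 | 50%, 50% | 0.323 vs 0.359 | 77.3% vs 80.1% | 3.3% vs 4.3% |
| 1.1 / 0.8 | 60%, 75% | 0.328 vs 0.354 | 77.4% vs 79.7% | 3.6% vs 4.4% |

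Power losses by subtraction are 0.3 to 0.6, 0.5 to 0.9 and 2.3 to 2.8 points. Relative attenuation (1 minus the ratio of the two log ORs) is about 1%, 3 to 4% and 7 to 10%. A model with the two main effects only had power within 0.1 point of the four-strata model.

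**The case against.** The strongest reply is that the intent is plain. The text promises both variables, SAP 1.5 lists four strata, and 7.1.3 calls the term 4-level. SAP 7.3.1 counts seven stratification variables and covariates, which fits six covariates plus one stratum factor. The code also leaves `sex` out of CLASS, so it can be read as a sketch, and a programmer who saw 1 df for a 4-level term would know what to correct. That is fair as to intent. It does not settle the matter, because 7.1.3 commits to the printed code and no other section overrides it.

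Several stronger readings are tempting, and the documents do not support them:
- **Both factors are wholly unadjusted.** This is exact only for equal strata. Otherwise the contrast absorbs part of each.
- **`thromb_app` is the device actually used.** SAP 7.1.3 names the first declared device as the adjuster. Its third supportive analysis substitutes the actual approach for the declared one, and Table 2 writes that model differently. So `thromb_app` elsewhere is the declared approach.
- **Every adjusted model is affected.** Only the primary code is binding. The shift-model code is an example, and the ANCOVA models in 7.3 have no code. Read with the note in 7.1.3, Table 2 can be taken as shorthand for the four strata.
- **The test is invalid.** The printed term's simulated type I error was 3.3% to 5.4% and never above that of the four-strata model. When the factors are strongly prognostic the test becomes conservative.

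The objection that the effect is small also stands. A separate run of 4,000 paired trials at the design odds ratio and the 60%/75% shares gave losses of 0.03, 0.2 and 1.6 points for alteplase odds ratios of 1.5, 2 and 3.

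**Conclusion.** The point holds as a mismatch between code and text in the primary model. As printed, the term carries 1 df where the text requires 3, and neither stratification factor has its own term. This rests on the code as printed and on full-rank coding of the two factors.

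The numerical consequence is modest: under about 1 point of power for weak to moderate prognostic effects and about 2 to 3 points for strong ones, with matching attenuation of the log odds ratio and no sign of type I error inflation. These figures depend on assumed shares and effects. They also assume near-exact balance within strata, which the biased-coin allocation only approximates. The attenuation comes from conditioning on less prognostic information in a logistic model; it is not confounding. The reason to act is that the pivotal analysis should have one unambiguous specification before unblinding.

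**What to change.** Before unblinding, replace `alteplase*thromb_app` in both code blocks by `alteplase|thromb_app` (main effects plus interaction), or by a single 4-level stratum variable listed in CLASS. Change Table 2 to the same notation, and use the same term in the re-randomization programs.

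As a minor clarification, define `alteplase` as the stratum value locked at randomization (SAP 1.5, Protocol 6.2). The present wording, treatment received, could differ for a subject whose alteplase status changed after randomization.

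The cost is a short SAP amendment and a one-term code edit. Sample size, data collection and trial conduct are unaffected.

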7.2 Secondary Efficacy Analyses

Descriptive summaries will be provided for each secondary endpoint in the ITT population. As with the primary endpoint, secondary endpoint analyses will also generally be adjusted for both the stratification variables and covariates used in the minimization algorithm.

All tests will be conducted with two-sided level of significance $\alpha = 0.05$. A fixed sequence multiple testing procedure will control the overall experiment-wise error rate for the trial (see below). It pre-specifies that, with all tests conducted at the same pre-specified significance level, the primary endpoint will be tested first, and all subsequent tests are considered failed and deemed exploratory if conducted, in the order specified (primary analysis first, key secondary analysis second, etc.), after the first test which fails. All tests that follow the first failed test, are considered exploratory. For the purpose of clarity, since the key secondary analysis of the ordinal mRS scores will employ a proportional odds model (POM), if test of the proportional odds assumption shows the assumption to be invalid, this key secondary analysis will not be performed, and the remaining secondary tests will still be considered to be protected.

The secondary endpoints, and the order they are to be tested, are:

1. Shift to reduced functional dependence analyzed across the whole distribution of scores on the mRS at Day 90 or the last rating.

2. Proportion of subjects with good neurological outcome, as defined by a score of 0-2 vs 3 or greater on the NIHSS at Day 90 or the last rating.
3. Proportion of subjects with functional independence in activities of daily living, as defined by a score of ≥ 95 vs 0-90 on the Barthel Index at Day 90 or the last rating.
4. The proportions of control and NA-1 treated subjects who die by study day 90.
5. The proportion of subjects with mRS score of 0-1 at Day 90.

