11.3 Analysis of Primary Efficacy Outcome

The primary efficacy outcome for the pivotal assessment of efficacy for regulatory purposes is the overall proportion subjects experiencing a favorable functional outcome 90-days post-randomization, defined as 0 to 2 on the mRS. These subjects are defined as responders. Subjects missing the day 90 primary assessment for any reason will be considered non-responders for the primary analysis (see [Section 11.8](#)). The primary hypothesis to be tested is that administration of NA-1 will result in an increase in the proportion of subjects with independent functioning on the mRS (as defined by a score of 0-2) at Day 90. The primary analysis will be a Wald test for treatment group difference in the primary outcome from a logistic regression adjusted for the 2 stratification variables (alteplase use, first declared thrombectomy device) and the 6 covariates used in the minimization: Age, sex, baseline NIHSS score, baseline ASPECTS score, occlusion

location and site. This will be conducted on the ITT population at the 2-sided 5% significance level overall (for the trial), adjusted for the interim analysis per the O'Brien-Fleming boundary spending function.

[figure not shown]
Three supportive analyses to the primary analysis will be conducted: (1) the primary analysis reapplied to the Per Protocol population; (2) a re-randomization analysis to demonstrate that minimization did not bias the primary endpoint analysis and (3) The primary analysis will be repeated on the PP population using actual first endovascular approach (instead of declared approach). Details of these are provided in the Statistical Analysis Plan.

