11.10 Independent Data Monitoring Committee

An IDMC will perform periodic safety reviews of the clinical data. The reviews will occur when 100, 300 and 600 subjects have reached their Day 90 final study visit.

An efficacy interim analysis after approximately 600 subjects complete the Day 90 follow-up will be conducted using the alpha spending function method¹ with O'Brien and Fleming² type stopping boundary for efficacy and a non-binding conditional power boundary for futility. The trial may be stopped for overwhelming efficacy or for futility at the interim analysis if the test statistic crosses the O-F or conditional power boundary. The IDMC charter will describe, among other

things, the approach to handling overwhelming efficacy, futility, and potential imbalance in key prognostic variables.

To prevent operational bias all interim results on safety and efficacy will be reported only to the IDMC, keeping the sponsor, project team, investigators and subject blind to results by treatment assignment during the study. Firewalls will be in place at the Statistical Analysis Center preparing all interim reports to protect and sequester all interim results on safety and efficacy. This will be detailed in the IDMC Charter.

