3.0 INTERIM EFFICACY ANALYSES

An efficacy interim analysis after approximately 600 subjects complete the Day 90 follow-up (~56% information) will be conducted by the unblinded statistician in the independent Statistical Group (ISG) using the alpha spending function method^[11] with O'Brien and Fleming^[12] type stopping boundary for efficacy and a non-binding conditional power boundary (based on the observed trend at the interim analysis) for futility. Overwhelming efficacy at the interim analysis would occur if the test statistic crosses the O-F superiority boundary. For an interim analysis conducted at exactly 55.8% information, the superiority critical p-value for stopping (boundary value) would be 0.003 and that at the end of the study (primary analysis) would be 0.024, 1-sided. Conversely if the conditional power estimate based on the observed trend at the interim is <1% the trial may be deemed to be futile, contingent on consideration of other safety and efficacy factors (i.e., the futility boundary is nonbinding).

The IDMC may recommend stopping for futility at the interim analysis if the test statistic crosses the O-F or conditional power boundary. However, notwithstanding the O-F superiority critical p-value of 0.003 for stopping (boundary value) at the interim analysis of the primary efficacy outcome, the IDMC will be instructed that it should not recommend to stop the trial for overwhelming efficacy unless otherwise instructed by the Steering Committee at the Open Session of the IDMC meeting. The IDMC Charter will provide further details on the rationale for, and how, these recommendations will be communicated.

To prevent operational bias all interim results on safety and efficacy will be reported only to the IDMC, keeping the sponsor, project team, investigators and subject blind to results by treatment assignment during the study. Firewalls will be in place at the Statistical Group preparing all interim reports to protect and sequester all interim results on safety and efficacy

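### SAP 7.2 and protocol 11.4 put every test at two-sided 0.05, which conflicts with the primary's O'Brien-Fleming levels and leaves the secondaries without a level for an early efficacy stop

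*SAP*

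**What the plan says.** The documents describe the level of the primary test in two ways.

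- **One common level.** SAP 7.2 opens its multiplicity paragraph with "All tests will be conducted with two-sided level of significance" at 0.05. It then describes the fixed sequence, "with all tests conducted at the same pre-specified significance level, the primary endpoint will be tested first". Protocol 11.4 carries the same text. Read literally, the primary is one of these tests. Both sections say the procedure controls the experiment-wise error rate.
- **Adjusted levels.** SAP 7.1.3 describes the level of the primary as "2-sided 0.05 significance level overall (for the trial), adjusted for the interim analysis per the O'Brien-Fleming boundary spending function". Protocol 11.3 has the same rule, worded as "2-sided 5% significance level overall (for the trial), adjusted for the interim analysis per the O'Brien-Fleming boundary spending function". SAP 3.0 assumes 55.8% information at the interim and gives these numbers: "the superiority critical p-value for stopping (boundary value) would be 0.003 and that at the end of the study (primary analysis) would be 0.024, 1-sided".

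SAP 6.0 also has a general default of two-sided 0.05, but qualifies it by allowing exceptions stated elsewhere.

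On early stopping, protocol 11.10 says: "The trial may be stopped for overwhelming efficacy or for futility at the interim analysis". SAP 3.0 is narrower. The IDMC is told not to recommend an efficacy stop unless the Steering Committee instructs otherwise at the Open Session. Neither document gives a secondary level other than two-sided 0.05, and neither says what applies to the secondaries if the trial stops at 600 subjects.

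**The concern.** Two questions follow.

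First, a pivotal primary test needs one final threshold. SAP 7.2 gives 0.05 two-sided. SAP 3.0 gives 0.024 one-sided, which is 0.048 two-sided. The result also decides whether any secondary can be claimed, so a p-value in the gap changes the whole confirmatory outcome.

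Second, a fixed sequence in a group-sequential trial does not automatically protect the secondaries when only the primary has a boundary. If the trial stops because the primary is extreme, a correlated secondary is tested at a look chosen for that extremeness. Testing it there at full alpha, with another chance at full alpha at the end on the paths that continue, can push its error above 2.5% one-sided. That would contradict the stated control of the overall error rate.

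**Working it through.** **Inputs.** Overall alpha 0.05 two-sided (0.025 in the favourable direction), from SAP 7.1.3. Interim at 600 of 1076 evaluable subjects, and 52% against 60.7% responders, from SAP 1.4 and 3.0. I take 1076 as the total (538 per arm), because 2 × 560 = 1120 is about 1.04 × 1076. The futility bound is non-binding, so it does not enter the alpha calculation. The documents give no correlation between endpoints, so those values are assumptions.

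**Step 1: reproduce the plan's boundaries.** Information fraction t = 600/1076 = 0.5576, √t = 0.7467. O'Brien-Fleming-type spending, one-sided 0.025:

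- Interim: 2 × [1 − Φ(2.2414/0.7467)] = 2 × [1 − Φ(3.0016)] = 0.00269, z = 2.784.
- Final: solve P(Z1 < 2.784, Z2 < c) = 0.975 with correlation 0.7467. This gives c = 1.975, p = 0.0241 one-sided, 0.0483 two-sided.

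These round to the stated 0.003 and 0.024. Power with these bounds is 81.8% (pooled variance), against 81.7% stated. The plan's figures stand.

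**Step 2: error of the primary under each reading (two-sided).**

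- SAP 3.0 and 7.1.3 as written: 5.00%.
- O'Brien-Fleming level at the interim, 0.05 at the end (SAP 7.2 taken literally for the final test): 2 × 0.02584 = 5.17%.
- Plain 0.05 at both looks: 8.1%. No section supports this, since SAP 3.0 fixes the interim level.

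The first two readings differ in their decision only for a final two-sided p between 0.0483 and 0.05.

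**Step 3: a first secondary with no true effect.** I simulated 4 million trials per case. The primary uses the bounds of step 1. At whichever look the primary first crosses, the trial ends and the secondary is tested at one-sided 0.025. Drift is the expected final z of the primary; the design effect gives 0.087/0.0301 = 2.89. Entries are one-sided error in percent, with Monte Carlo error about 0.01.

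| Assumed correlation | Drift 1.0 | Drift 1.4 | Drift 2.89 (design) |
|---|---|---|---|
| 0.5 | 1.60 | 2.07 | 2.79 |
| 0.7 | 2.32 | 2.71 | 2.88 |
| 0.8 | 2.71 | 3.01 | 2.85 |
| 0.9 | 3.13 | 3.35 | 2.78 |
| 1.0 | 3.73 | 3.74 | 2.64 |
| Chance the primary crosses at 600 | 2 | 4 | 26 |

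**Step 4: the same secondary under other rules.**

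- No efficacy stop, secondary tested once at the end at 0.025: at most 2.5% in every case, apart from Monte Carlo error.
- Efficacy stop allowed, O'Brien-Fleming-type bounds applied to the secondary as well (0.0027 and 0.0241): at or below 2.5% in every case. At the design effect it is 0.5-1.2% for correlations 0.5-0.9, so this rule is conservative.

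**The case against.** A reader might infer from SAP 7.2 that the plan ignores the O'Brien-Fleming levels and so loses control of the primary's error. The documents do not support that. SAP 3.0, SAP 7.1.3 and protocol 11.3 all apply the adjustment, and under them the error is 5.0%. The common-level text sits in the secondary-endpoint sections and can be read as naming the overall alpha. This disposes of the stronger reading. It does not remove the conflict, because the sentence names the primary and says all tests share one level.

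On the secondaries, the case against is substantial:

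- The SAP's default is that no efficacy stop is recommended, and SAP 8.5 sequesters the unblinded group from the Steering Committee. Under that default there is no inflation. The path stays open, however, in protocol 11.10 and by Steering Committee instruction.
- No section says the secondaries would be tested at 600 subjects. After a stop, the data could include subjects already enrolled and still in follow-up, and the IDMC Charter may add rules. The gap is therefore one of silence.
- The largest errors need a small primary effect and a very high correlation, where crossing at 600 is rare (2-4%). They must not be paired with the 26% chance, which belongs to the design effect and its 2.8-2.9%.
- For the shift analysis, a common odds ratio of 1 would also mean no effect on mRS 0-2. An effective primary with a null shift therefore contradicts the model. This weakens the scenario for the key secondary, but not for NIHSS 0-2, which follows it and becomes the first secondary if the proportional-odds check fails.
- Later secondaries face more gates than the simulated one.

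These points limit the size and likelihood of the problem. They do not supply the missing level.

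**Conclusion.** The point holds as a conflict of wording plus a gap, of minor to moderate severity.

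- **Primary.** Two final thresholds stand in the documents, 0.05 and about 0.048 two-sided. The consequence is 5.17% against 5.0% overall error and a narrow band of p-values with opposite conclusions. It would be wrong to say that the plan fails to control the primary's error, because the sections defining that test do control it.
- **Secondaries.** The claim of overall error control is unsupported only if an efficacy stop at 600 is taken and the secondaries are tested at that look at two-sided 0.05. A null first secondary then has one-sided error of about 2.8-2.9% at the design effect (assumed correlation 0.5-0.9) and roughly 3.3-3.7% at smaller primary effects (assumed correlation 0.9-1.0), against 2.5%. With no early efficacy stop it stays at 2.5%.

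The figures rest on normal approximations, the assumed correlations, and a secondary with no true effect alongside an effective primary.

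**What to change.** In SAP 7.2 and protocol 11.4, replace the common-level text so that it states:

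1. Two-sided 0.05 is the overall level for the trial.
2. The primary is tested at its O'Brien-Fleming-adjusted level: about 0.0027 one-sided at 600 subjects and 0.0241 at the end, recalculated at the actual information fraction.
3. After an early efficacy stop, each secondary in the sequence is tested at a pre-specified group-sequential boundary for that look, and not at full 0.05. The same O'Brien-Fleming-type spending boundary is sufficient; another spending function could be chosen.
4. At the final analysis the secondaries may stay at two-sided 0.05 if no efficacy stop can be taken. Otherwise they use their own spending boundary.

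Point 4 requires protocol 11.10 and SAP 3.0 to agree on whether an efficacy stop is possible. The change must be made before unblinding.

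**Cost.** Wording only. Sample size, data collection and the primary's power do not change, because the stated power already reproduces with the adjusted levels. The real price is on the secondaries: with O'Brien-Fleming-type spending, a test after an early stop is at 0.0027 instead of 0.025 one-sided, about nine times stricter (0.025/0.0027 ≈ 9). At the end it is 0.0241 instead of 0.025.
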